10.5.2.4 Other safety data

Vital signs

The parameters collected are: height (cm), weight (kg), body temperature (°C), heart rate (beats per minute), systolic and diastolic blood pressure (mmHg).

The criteria for clinically notable abnormalities are defined as follows:

Clinically notable elevated values

- Systolic BP: ≥ 180 mmHg and an increase ≥ 20 mmHg from baseline
- Diastolic BP: ≥ 105 mmHg and an increase ≥ 15 mmHg from baseline.
- Body temperature: $\geq 39.1^{\circ}\text{C}$
- Weight: Increase from baseline of $\geq 10\%$
- Heart rate: ≥ 120 bpm with increase from baseline of ≥ 15 bpm

Clinically notable below normal values

- Systolic BP: ≤ 90 mmHg and a decrease ≥ 20 mmHg from baseline
- Diastolic BP: ≤ 50 mmHg and a decrease ≥ 15 mmHg from baseline
- Body temperature: $\leq 35^{\circ}\text{C}$
- Weight: decrease from baseline of $\geq 10\%$
- Heart rate: ≤ 50 bpm with decrease from baseline of ≥ 15 bpm

The following summaries will be produced for each vital sign parameter:

- Summary statistic for change from baseline to the worst post-baseline value (in both directions, i.e. from baseline to highest post baseline and from baseline to lowest post-baseline value),
- Number and percentage of patients with at least one post-baseline vital sign abnormality (in both directions, i.e. both elevated and below normal values).

All vital sign assessments will be listed by vital sign parameter. Clinically notable values will be flagged on listings.

10.5.3 Resource utilization

Not applicable

10.5.4 Patient-reported outcomes

Cushing's syndrome HRQoL questionnaire

A 12-item Cushing's syndrome HRQoL questionnaire (CushingQoL) is implemented in this trial. Raw summative scores are calculated and standardized on a by-patient and visit basis.

Patients who completed 9 or more items at an assessment are considered evaluable for that visit. Standardized scores and their changes from baseline to each scheduled post-baseline assessment will be descriptively summarized.

[figure not shown]
[figure not shown]
Work Productivity and Activity Impairment-General Health (WPAI-GH) questionnaire

[figure not shown]
The WPAI-GH yields four types of scores:

1. Absenteeism (work time missed)
2. Presenteeism (impairment at work / reduced on-the-job effectiveness)
3. Work productivity loss (overall work impairment / absenteeism plus presenteeism)
4. Activity Impairment

WPAI-GH scores are based on 1-item (presenteeism, activity impairment), 2-items (absenteeism) and multiple items (overall work productivity); a score will not be calculated if there is a missing response to the corresponding item. For example, an analysis of absenteeism would include only those subjects with responses to hours missed and to hours worked.

WPAI-GH scores and their changes from baseline to each scheduled post-baseline assessment will be descriptively summarized.

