4.12.1.2 CI for continuous variables

Two sided 95%Confidence Interval for continuous variable will be based on the t-distribution. The respective N, Mean and Standard error are outputted in to a data-step and then the TINV function is used to calculate the Confidence Interval as follows:

```
PROC MEANS DATA=test NOPRINT ;
  VAR age ;
  OUTPUT OUT=xxtmp N=n MEAN=mean STDERR=stderr ;
  RUN ;

  DATA xxtmp1 ; SET xxtmp ;
  lo = mean - ( TINV ( 0.95 , n-1 ) * stderr ) ;
  hi = mean + ( TINV ( 0.95 , n-1 ) * stderr ) ;
  RUN ;
```

5 Statistical methods and data analysis

Categorical data will be presented as frequencies and percentages. For continuous data, mean, standard deviation, median, minimum, and maximum will be presented.

A missing category for categorical data will be presented where applicable. Unless otherwise noted, percentages will be based on the number of patients in the relevant population or subgroup.

Whenever possible, minimum and maximum will be presented to the same precision as the raw data. Mean and median will be presented to one more decimal place and standard deviation to two more decimal places.

Unless noted otherwise, no imputation for missing data will be performed.

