. For example, if a patient answers all 12 items with 'Sometimes' or 'Somewhat', X = 36 and $Y = 100 \cdot 24/48 = 50$.

Similar analyses as defined above will also be performed at all other scheduled post-baseline assessments.

Changes from baseline to Week 12 , 24 and 48 in WPAI-GH scores

The WPAI-GH questionnaire is to assess work productivity and activity impairment.

WPAI outcomes are expressed as impairment percentages, with higher numbers indicating greater impairment and less productivity, i.e., worse outcomes, as follows (see [Reilly 2002](#)):

Questions:

- 1 = currently employed
- 2 = hours missed due to health problems
- 3 = hours missed other reasons
- 4 = hours actually worked
- 5 = degree health affected productivity while working
- 6 = degree health affected regular activities

Scores (multiply scores by 100 to express in percentages):

Percent work time missed due to health: $Q2/(Q2+Q4)$

Percent impairment while working due to health: $Q5/10$

Percent overall work impairment due to health:

$Q2/(Q2 + Q4)+[(1 - Q2/(Q2 + Q4)) \cdot (Q5/10)]$

[figure not shown]
Percent activity impairment due to health: $Q6/10$

Descriptive summaries of actual and percentage change in mean scores from baseline to Week 12, 24 and 48 will be provided. Similar analyses will also be performed at all other scheduled post-baseline assessments.

Changes from baseline in GH and IGF-I to Week 12, 24 and 48

Descriptive summaries of the absolute and relative change from baseline of GH and IGF-I at Week 12, 24 and 48 will be provided.

Similar analyses will also be performed at all other scheduled post-baseline assessments.

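### If Q5 is left blank by a patient who worked no hours because of health, the protocol's missing-item rule drops a WPAI overall work impairment score that the SAP formula fixes at 100%

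*Protocol*

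**What the plan says.** Change in WPAI-GH scores at Weeks 12, 24 and 48 is a secondary endpoint (protocol Table 3-1), summarised descriptively.

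Protocol Section 10.5.4 describes four scores. The overall work score rests on "multiple items (overall work productivity"), and the rule for incomplete questionnaires is that "a score will not be calculated if there is a missing response to the corresponding item". The one worked example is for a different score: "an analysis of absenteeism would include only those subjects with responses to hours missed and to hours worked".

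SAP Section 5.2.1 lists the items, including "2 = hours missed due to health problems", "4 = hours actually worked" and "5 = degree health affected productivity while working". Its overall work impairment formula begins "Q2/(Q2 + Q4)+[(1 - Q2/(Q2 + Q4" and continues by multiplying the bracketed remainder by Q5/10. Higher values are worse, so 100% is the worst score. The WPAI text in the SAP neither repeats the missing-item rule nor treats Q4 = 0 separately. The default at the start of SAP Section 5 is: "Unless noted otherwise, no imputation for missing data will be performed".

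**The concern.** Q5 asks about productivity during work. A patient on full sick leave in the recall period has no work to rate, so a blank Q5 is a natural response. The overall score lists Q5 among its inputs, so the protocol rule would withhold it. Yet in exactly this case Q5 has no weight in the SAP formula, and the score is known from the two items that were answered.

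Two patients with the same hours missed and worked would then be treated differently (one counted at 100%, one absent) because of an answer that cannot affect the result. The scores lost in this way are all at the bad end of the scale. The same patients stay in the absenteeism summary at 100%, so the two reported means would cover different patients. Within a patient, overall impairment is absenteeism plus a non-negative term and cannot be lower than absenteeism. The reported means could nevertheless appear in the opposite order.

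**Working it through.** The plan gives no numerical WPAI result to reproduce, so the check evaluates the SAP formula and then the effect of losing scores.

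**1. The formula when no hours were worked.** Write A = Q2/(Q2 + Q4) and overall = A + (1 − A) × Q5/10. With Q4 = 0 and Q2 > 0, A = 1, so overall = 1 + 0 × Q5/10 = 100%. Evaluating it for Q2 = 1, 8, 20 and 40 hours and every Q5 from 0 to 10 gives 100% each time. As a control, Q2 = 10, Q4 = 30, Q5 = 4 gives 0.25 + 0.75 × 0.4 = 55%, so Q5 does matter once some hours are worked.

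**2. What the missing-item rule does.**
- Q5 answered: the score is calculated as 100% and nothing is lost.
- Q5 blank: the rule read literally gives no score, and the SAP states no exception.
- Absenteeism is 100% in both cases, since it needs only Q2 and Q4. Activity impairment uses Q6 and is unaffected.

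**3. Effect on a visit mean.** Let s be the share of employed respondents with Q2 > 0 and Q4 = 0, m the mean overall score in the others, and f the fraction of the s group with Q5 blank. None of the three is in the documents; the values below are assumptions.

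- Full mean = 100s + m(1 − s)
- Reported mean = [100s(1 − f) + m(1 − s)] / (1 − sf)
- With f = 1 the shift is −s(100 − m); with f = 0 it is 0.

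| s | m | Full mean | Reported, f = 0.5 (shift) | Reported, f = 1 (shift) |
|---|---|---|---|---|
| 5% | 30 | 33.5 | 31.8 (−1.7) | 30.0 (−3.5) |
| 10% | 30 | 37.0 | 33.7 (−3.3) | 30.0 (−7.0) |
| 5% | 50 | 52.5 | 51.3 (−1.2) | 50.0 (−2.5) |
| 10% | 50 | 55.0 | 52.6 (−2.4) | 50.0 (−5.0) |

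**4. Effect on mean change.** Take 60 employed patients, of whom 54 go from 50 to 40 (change −10) and 6 are affected with Q5 blank (illustrative figures). In both cases below the plan reports −10.0 from the 54.
- The 6 move into full sick leave, 75 to 100: true mean change = (54 × −10 + 6 × 25)/60 = −6.5. The plan overstates improvement.
- The 6 move out of full sick leave, 100 to 75: true mean change = (54 × −10 + 6 × −25)/60 = −11.5. The plan understates improvement.

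**5. A neighbouring case.** Q2 = Q4 = 0 gives 0/0. The formula is undefined there, and the SAP does not mention it.

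**The case against.** The strongest reply is that nothing may be lost at all. Neither document reproduces the questionnaire or any instruction to skip Q5 when no hours were worked, and the SAP takes its scoring from a cited external source that cannot be checked here. The protocol's only example of the missing-item rule is absenteeism, and its reference to the corresponding item could be read as excluding an item with no weight. Impact is limited too: this is one of four WPAI scores, in a single-arm study with no hypothesis tests, and full sick leave remains visible in absenteeism.

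Most of this stands, and it rules out three stronger readings that a reader might infer:

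- *Every employed patient with zero hours worked has a missing overall score.* The plan does not say so. The loss needs a blank Q5.
- *The missing scores are simply the worst scores.* A patient with Q2 = 0, Q4 = 40 and Q5 = 10 scores 0 + 1 × 1 = 100% and is kept. The loss follows from zero hours worked with Q5 blank, not from the maximum as such.
- *The plan will show false improvement.* The direction for mean change depends on whether patients enter or leave full sick leave, and the documents do not say which is more common.

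The conflict itself is not answered. Once Q5 is blank, one document withholds a score that the other determines exactly, and no text reconciles them. The no-imputation default is no barrier to a fix, because a value that follows from answered items is computed, not imputed.

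**Conclusion.** The point holds conditionally. When Q2 > 0, Q4 = 0 and Q5 is blank, the missing-item rule discards an overall work impairment score whose value is known to be 100%. Any such loss lowers the visit mean, since only values of 100 are removed. Its effect on mean change has no fixed sign.

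The size cannot be established from the documents. It is zero if all such patients answer Q5. With 5-10% of employed respondents fully off work, all with Q5 blank, and a mean of 30-50 in the rest, the visit mean is 2.5 to 7 points too low. If half leave Q5 blank, the same inputs give about 1.2 to 3.3 points.

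This is a scoring gap in one descriptive secondary score. It does not touch the primary safety analysis, but it should be closed because the correct value is available at almost no cost.

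**What to change.** Add to the WPAI-GH scoring in SAP Section 5.2.1:

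> If Q2 > 0 and Q4 = 0, percent overall work impairment is 100% whether or not Q5 is answered; percent impairment while working is not applicable if Q5 is blank.

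Keep the missing-item rule for all other cases. The rule agrees with the existing formula for every possible Q5, so it cannot introduce error. It would help to state in the same place how Q2 = Q4 = 0 is handled, since the formula gives no value there.

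The cost is one sentence in the SAP and one line of scoring code, with no new data. The SAP should note that this clarifies protocol Section 10.5.4. Putting the sentence in the protocol as well would need a written amendment under protocol Section 12.1, which the point does not seem to warrant.

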10.7 Interim analysis

No formal interim analysis is planned. However, since the timing of drug approval may differ between regions, data from a specific region may be reported when all patients from that region have been followed for 28 days after they have either prematurely discontinued pasireotide s.c. or after completing treatment as per protocol (i.e. when the study drug is approved for commercial use and reimbursed in each respective country or until 31 December 2015 (until 31 December 2016 for sites in South Korea and Brazil), whichever occurs first). For regulatory purposes, at time of a regional interim analysis, data from countries where the trial is still ongoing maybe included. Furthermore, independent of a regional interim analysis additional interim analysis may be performed for regulatory purpose or publication purpose and details will be specified in the study's analysis plan.

10.8 Sample size calculation

No sample size calculation was performed. The planned sample size of approximately 200 patients was chosen based on the expected accrual rates and planned duration of the trial. The actual sample size may differ from this planned numbers.

10.9 Power for analysis of key secondary variables

Not applicable.

11 Ethical considerations and administrative procedures

11.1 Regulatory and ethical compliance

This clinical study was designed, shall be implemented and reported in accordance with the ICH Harmonized Tripartite Guidelines for Good Clinical Practice, with applicable local regulations (including European Directive 2001/20/EC and US Code of Federal Regulations Title 21), and with the ethical principles laid down in the Declaration of Helsinki.

11.2 Responsibilities of the investigator and IRB/IEC/REB

The protocol and the proposed informed consent form must be reviewed and approved by a properly constituted Institutional Review Board/Independent Ethics Committee/Research Ethics Board (IRB/IEC/REB) before study start. A signed and dated statement that the protocol and informed consent have been approved by the IRB/IEC/REB must be given to Novartis before study initiation. Prior to study start, the investigator is required to sign a protocol signature page confirming his/her agreement to conduct the study in accordance with these documents and all of the instructions and procedures found in this protocol and to give access to all relevant data and records to Novartis monitors, auditors, Novartis Clinical Quality Assurance representatives, designated agents of Novartis, IRBs/IECs/REBs and regulatory authorities as required.

11.3 Informed consent procedures

Eligible patients may only be included in the study after providing written (witnessed, where required by law or regulation), IRB/IEC/REB-approved informed consent or, if incapable of doing so, after such consent has been provided by a legally acceptable representative of the patient. In cases where the patient's representative gives consent, the patient should be informed about the study to the extent possible given his/her understanding. If the patient is capable of doing so, he/she should indicate assent by personally signing and dating the written informed consent document or a separate assent form. Informed consent must be obtained before conducting any study-specific procedures (i.e. all of the procedures described in the protocol). The process of obtaining informed consent should be documented in the patient source documents. The date when a subject's Informed Consent was actually obtained will be captured in their CRFs.

Novartis will provide investigators in a separate document with a proposed informed consent form (ICF) that is considered appropriate for this study and complies with the ICH GCP guideline and regulatory requirements. Any changes to this ICF suggested by the investigator must be agreed to by Novartis before submission to the IRB/IEC/REB, and a copy of the approved version must be provided to the Novartis monitor after IRB/IEC/REB approval.

Women of child bearing potential should be informed that taking the study medication may involve unknown risks to the fetus if pregnancy was to occur during the study and agree that in order to participate in the study they must adhere to the contraception requirement for the duration of the study. If there is any question that the patient will not reliably comply, they should not be entered in the study.

11.4 Discontinuation of the study

[figure not shown]
Novartis reserves the right to discontinue this study under the conditions specified in the clinical study agreement. Specific conditions for terminating the study are outlined in [Section 4.4](#).

11.5 Publication of study protocol and results

Novartis assures that the key design elements of this protocol will be posted in a publicly accessible database such as clinicaltrials.gov. In addition, upon study completion and finalization of the study report the results of this study will be either submitted for publication and/or posted in a publicly accessible database of clinical study results. Different publications of the data are planned. Regional and/or country population analysis and publication will be allowed after the analysis and presentation of the multinational (or global) population is performed.

11.6 Study documentation, record keeping and retention of documents

Each participating site will maintain appropriate medical and research records for this trial, in compliance with Section 4.9 of the ICH E6 GCP, and regulatory and institutional requirements for the protection of confidentiality of subjects. As part of participating in a Novartis-sponsored study, each site will permit authorized representatives of the sponsor(s)

and regulatory agencies to examine (and when required by applicable law, to copy) clinical records for the purposes of quality assurance reviews, audits and evaluation of the study safety and progress.

Source data are all information, original records of clinical findings, observations, or other activities in a clinical trial necessary for the reconstruction and evaluation of the trial. Examples of these original documents and data records include, but are not limited to, hospital records, clinical and office charts, laboratory notes, memoranda, subjects' diaries or evaluation checklists, pharmacy dispensing records, recorded data from automated instruments, copies or transcriptions certified after verification as being accurate and complete, microfiches, photographic negatives, microfilm or magnetic media, x-rays, and subject files and records kept at the pharmacy, at the laboratories, and medico-technical departments involved in the clinical trial.

Data collection is the responsibility of the clinical trial staff at the site under the supervision of the site Principal Investigator. The study CRF is the primary data collection instrument for the study. The investigator should ensure the accuracy, completeness, legibility, and timeliness of the data reported in the CRFs and all other required reports. Data reported on the CRF, that are derived from source documents, should be consistent with the source documents or the discrepancies should be explained. All data requested on the CRF must be recorded. Any missing data must be explained. For electronic CRFs an audit trail will be maintained by the system. The investigator/institution should maintain the trial documents as specified in Essential Documents for the Conduct of a Clinical Trial (ICH E6 Section 8) and as required by applicable regulations and/or guidelines. The investigator/institution should take measures to prevent accidental or premature destruction of these documents.

Essential documents (written and electronic) should be retained for a period of not less than fifteen (15) years from the completion of the Clinical Trial unless Sponsor provides written permission to dispose of them or, requires their retention for an additional period of time because of applicable laws, regulations and/or guidelines.

11.7 Confidentiality of study documents and patient records

[figure not shown]
The investigator must ensure anonymity of the patients; patients must not be identified by names in any documents submitted to Novartis. Signed informed consent forms and patient enrollment log must be kept strictly confidential to enable patient identification at the site.

11.8 Audits and inspections

Source data/documents must be available to inspections by Novartis or designee or Health Authorities.

11.9 Financial disclosures

Financial disclosures should be provided by study personnel who is directly involved in the treatment or evaluation of patients at the site - prior to study start.

[figure not shown]

12 Protocol adherence

Investigators ascertain they will apply due diligence to avoid protocol deviations. Under no circumstances should the investigator contact Novartis or its agents, if any, monitoring the study to request approval of a protocol deviation, as no authorized deviations are permitted. If the investigator feels a protocol deviation would improve the conduct of the study this must be considered a protocol amendment, and unless such an amendment is agreed upon by Novartis and approved by the IRB/IEC/REB it cannot be implemented. All significant protocol deviations will be recorded and reported in the CSR.

Version	Date	Changes
2.0	11-Nov-2011	Initial version
2.1	13-June-2012	
Biomarker section modified: Hscores for Immunohistochemistry added
 
Incorporation of changes made after Protocol amendment 3
 
Objectives and Endpoints
 
As a consequence of extending the study duration, objectives and endpoints have been updated to include an additional time point for analysis at week 48.
 
Description of Study Design
 
This section has been updated to reflect the changes of the starting dose in the European Union and the change of study duration.
 
Subgroup analysis
 
In this section an additional analysis by starting dose has been added.
 
(Adding week 48, starting dose)

2.2	22-July-2012	Revision after 2 nd RAP II meeting (visit windows, dose calculation, biomarker section)
3.0	26-Sep-2012	
Final version, Amendment 1
 
Revision after LF review
 
Mean daily dose grouping has been added.
 
Section 4.4 Visit window has been added.
 
Section 4.9 Calculation of changes has been added.
 
Section 4.10 Dose calculations has been added
 
Section 4.12.1.2 CI for continuous variable has been added.

3.1	26- Oct -2012	Removed “Normally Distributed” from section 4.12.1.2
3.2	29-Sep-2016	
Draft version , Amendment 2
 
Added Mean 24h-UFC calculation section: the mean UFC calculation at week 12,24and 48 will be based on the last two or three samples collected before the visit , instead of considering only three samples
 
Update sample size calculation
 
Added the publication purposes in the interim analysis
 
Removed biomarker data analysis due to the fact that the vendor never analyzed the data collected for only 7 patients due to Novartis decision

3.3	10-Mar-2017	Final version , Amendment 2

1 Introduction

The RAP document describes the planned statistical analyses for the clinical study report for study SOM230B2406 in the treatment of Cushing's disease. SAS® version 9.4 (SAS Institute Inc., Cary, NC, USA) or later will be used for all analyses. Any changes made to this statistical plan after the clinical database lock will be documented separately.

Even written before database lock, this document is using past tense in order to simplify the CSR writing.

2 Study design and treatment

This study is an open-label, uncontrolled, single-arm, multi-center, multi-national expanded access study of pasireotide sub-cutaneous administered twice a day in patients with persistent or recurrent Cushing's disease or with de novo Cushing's disease that are not considered candidates for pituitary surgery (confirmed Cushing's disease).

The starting dose depends on the location of the site:

For sites located in the European Union: the starting dose is 600 µg b.i.d. . However, patients already enrolled in the study at the time of the approval of the amendment 3 are to continue on their current assigned dose.

For site located outside the European Union: the starting dose is 900 µg b.i.d. in all patients except for those with impaired glucose metabolism for whom the starting dose is 600 µg b.i.d.

After a 21-day screening period, patients who satisfied all the inclusion/exclusion criteria started receiving pasireotide. During the first 24-week period, patients had a visit on a weekly basis up to week 4 and then on a 4-week basis. In the second study period, i.e. after the 24 week visit, visits are taking place on 12-week intervals until the end of the study.

Patients remained in the study until pasireotide is approved for commercial use and reimbursed in each respective country or until 31 December -2015 (until 31 December 2016 for sites in South Korea and Brazil), whichever occurred first.

3 Objectives

